#### **9.4 Serious Adverse Event Reporting Procedures**

Study site personnel must notify Lilly or its designee of any SAE within 24 hours of investigator awareness of the event via a Lilly-approved method. If alerts are issued via telephone, they are to be immediately followed with official notification on study-specific SAE forms. This 24-hour notification requirement refers to the initial SAE information and all follow-up SAE information.

#### **9.5 Complaint Handling**

Lilly collects product complaints on investigational products and drug delivery systems used in clinical studies in order to ensure the safety of study participants, to monitor quality, and to facilitate process and product improvements.

Patients will be instructed to contact the investigator as soon as possible if he or she has a complaint or problem with the investigational product so that the situation can be assessed.

## **10.0 STATISTICAL CONSIDERATIONS**

### **10.1 Trial Design**

This is an open-label, randomized, multicenter, Phase 2 trial in adult male and female patients with treatment-naïve, Stage IV/metastatic NSCLC whose tumors are not known to have any EGFR mutation or ALK rearrangement and have negative or low expression (0% to 49%) of PD-L1 as determined by any FDA-approved PD-L1 assay.

Patients will be stratified according to tumor histology (squamous vs non-squamous) and smoking history (current smokers vs former smokers vs never smokers). Current smokers will include patients who are currently using any form of tobacco, former smokers will include patients with a prior history of any form of tobacco use, and never smokers will include patients with no history of any form of tobacco use.

Patients will be randomized in a 1:1 ratio into 1 of 2 treatment arms.

- **Arm 1:** Patients will receive AM0010 as a SQ QD) injection plus nivolumab as IV infusion on Day 1 of a 14-day cycle or 28-day cycle.
- **Arm 2:** Patients will receive nivolumab as IV infusion on Day 1 of a 14-day cycle or 28-day cycle.

### **10.2 Trial Endpoints**

#### **10.2.1 Primary Endpoint**

- **Objective Response Rate**

The ORR is defined as the proportion of patients with a confirmed CR or PR relative to the efficacy population. The ORR is determined by the best response designation per RECIST v1.1 recorded between the date of randomization and the date of objectively documented progression or the date of subsequent anti-cancer therapy, or death, whichever occurs first. For patient without documented progression or subsequent anti-cancer therapy, all available response designations will contribute to the ORR determination. Confirmed responses are those that persist on repeat imaging scan  $\geq 4$  weeks after initial documentation of response. For patients who continue treatment beyond progression due to suspected pseudoprogression as outlined in Section 7.6. The objective response should be determined based on response assessment recorded at the CT scan done no less than 4 weeks after suspected pseudoprogression. If the patient subsequently responds or returns to baseline, that assessment of objective tumor response is achieved after pseudoprogression as the true response per RECIST v.1.1.

#### **10.2.2 Secondary Endpoints**

- **Progression-Free Survival**

Progression-free survival is defined as the time from randomization to the date of the first documented tumor progression as determined by the Investigator (per RECIST v.1.1 criteria or clinical progression) or death due to any cause whichever occurs first. Patients who

experience clinical disease progression should undergo scanning to document radiographic disease progression per RECIST v.1.1. In this case, the date of the confirmatory CT scan will be used as the date of disease progression. Patients who die without a reported prior progression will be considered to have progressed on the date of their death. Patients who did not progress or die will be censored on the date of their last tumor assessment. Patients who did not have any on-trial tumor assessment and did not die will be censored on the date they were randomized with a duration of 1 day. Patients who received any subsequent anti-cancer therapy without a prior documented progression will be censored at the last tumor assessment prior to initiation of the subsequent anti-cancer therapy. Any additional censoring rules that may be needed will be specified in the statistical analysis plan.

- **Overall Survival**

Overall survival is defined as the time from the date of randomization to the date of death. Patients who are no longer on trial treatments should be followed for survival. A patient who is alive will be censored at the date last known to be alive.

- **Disease Control Rate**

Disease control rate is defined as the proportion of patients who achieve SD $\geq$ 9 weeks ( $\pm$ 7 days) plus confirmed CRs + confirmed PRs as determined by the Investigator using RECIST v.1.1.

- **Duration of Response**

Duration of response (DoR) is defined as the time from the date of the first documentation of objective tumor response (CR or PR) to the date of the first documentation of objective tumor progression or death due to any cause, whichever occurs first.

### **10.3 Sample Size Considerations**

Approximately 50 patients will be randomized to the 2 treatment arms in a 1:1 ratio. With a total of 50 patients, 25 patients each arm would enable evaluating ORR for each treatment arm. With 25 patients in each treatment arm, the 90% confidence interval for an objective response rate would be (3%, 28%) if 3 patients (12%) had a response; (11%, 42%) if 6 patients (24%) had a response; and (17%, 50%) if 8 patients (32%) had a response..

### **10.4 Analysis Population**

- All Enrolled Patients: all patients who signed an informed consent form and were registered into the interactive Web-response system (IWRS).
- ITT Population: All patients who are randomized. This is the primary population for analyses of efficacy and baseline characteristics.
- Safety Population: All randomized patients who received any amount of study drug. This is the primary population for exposure and safety.
- PK Population: All treated patients with available serum time-concentration data from randomized patients dosed with AM0010.

- Biomarker Population: All treated patients with available biomarker data from randomized patients.

## **10.5 Planned Method of Analysis**

### **10.5.1 General Approach/Considerations**

Unless otherwise stated, descriptive statistics will be provided for all endpoints for each treatment group and overall. Continuous measurements will be summarized using the mean, standard deviation, median, interquartile range, range, and number of patients.

All efficacy analyses will be stratified by the histology type at randomization.

### **10.5.2 Demographic and Baseline Characteristics**

Demographics (age, sex, and race) and other baseline disease characteristics will be summarized using descriptive statistics.

### **10.5.3 Efficacy Analyses**

#### **10.5.3.1 Primary Efficacy Analyses**

Objective response rate is defined as the proportion of patients who achieve confirmed CR+PR. Objective response rate and the corresponding 95% exact CI will be calculated by Clooper-Pearson method for each randomized arm.

#### **10.5.3.2 Secondary Efficacy Analyses**

Progression-free survival time will be summarized using Kaplan-Meier method to estimate the median PFS and 95% confidence interval (CI).

Overall survival will be summarized using Kaplan-Meier method to estimate the median PFS and 95% confidence interval (CI).

The DCR will be analyzed in the same manner as objective tumor response.

Duration of response is defined as the time from the date of the first documentation of objective tumor response (CR or PR), as determined by the Investigator using RECIST v.1.1, that is subsequently confirmed to the date of the first documentation of objective tumor progression or to death due to any cause, whichever occurs first. Duration of response will be censored on the date of the last tumor assessment on trial for patients who do not have objective tumor progression and who do not die due to any cause while on trial. For patients who have an ongoing objective response but discontinued to have tumor scans assessments before disease progression, the duration of response will be censored at the date of the last tumor assessment.

Duration of response will be estimated for each treatment arm using the Kaplan-Meier product-limit method for patients who have CR or PR. Duration of SD will be summarized as well.

Time to response is defined as the time from date of randomization to the date of the first documentation of objective tumor response that is subsequently confirmed. Duration of

response and time to response will only be evaluated in patients with objective response of CR or PR and will be summarized by trial treatment arm.

#### **10.5.4 Safety Analyses**

All safety summaries and analyses will be performed on the Safety Population.

Safety and tolerability will be measured by:

- Adverse events
- Physical examinations (including neurological examination)
- Vital signs
- ECGs
- Laboratory assessments
  - Hematology
  - Chemistry
  - Coagulation tests
  - Thyroid function
  - Urinalysis

#### **10.5.5 Extent of Exposure**

Extent of exposure will be summarized, variables include duration of treatment, number of cycles, total dose administered, and relative dose intensity for the entire treatment duration as well as for each cycle. Number and percentage of patients experiencing dose modifications for each treatment arm, and reasons will be provided as well.

#### **10.5.6 Adverse Events**

Adverse events will be analyzed in terms of treatment-emergent AEs defined to be any AEs that begin or worsen in intensity after trial drug initiation through 30 days after the last dose of trial drug. All AEs will be coded based on MedDRA terms.

Descriptive statistics of safety will be presented using NCI-CTCAE version 4.03 by treatment arm. All treatment emergent AEs, treatment-related AEs, SAEs, treatment-related SAEs, and AEs leading to discontinuation from the trial treatments will be tabulated using the worst grade per NCI-CTCAE v4.03 criteria by system organ class and preferred term. Additional summaries include AEs by intensity (Grade 1 to 4 or/and Grades 3 and 4).

Non-treatment emergent AEs arising from screening procedures or occurring more than 30 days after the last dose will be summarized or listed.

#### **10.5.7 Clinical Laboratory Data**

Summary and change in laboratory data will be provided over time for hematology, chemistry parameters, and urinalysis.

The NCI-CTCAE v4.03 grade for selected hematology parameters will be summarized by the worst grade in each treatment cycle and the worst grade during the trial for each treatment arm. The number and percent of patients with NCI-CTCAE v4.03 hematology value of

Grade 3 or 4 that occur after the first dose of trial drugs also will be presented. Shift tables may be provided.

Liver and renal function will be summarized using NCI-CTCAE v4.03 grade for selected chemistry parameters. The number and percent of patients with NCI-CTCAE v4.03 chemistry values of Grade 3 or 4 that occur after the first dose of trial drugs also will be presented. Shift tables may be provided.

#### **10.5.8 ECOG Performance Status**

Descriptive statistics will be provided for ECOG performance status at each assessment time.

#### **10.5.9 Vital Signs**

Vital signs (blood pressure, heart rate, temperature, and oxygen saturation), weight, and change from baseline will be summarized by treatment arm.

#### **10.5.10 12-Lead ECG**

The ECG parameters including QTc and change from baseline will be summarized by visit and by treatment arm.

Number and percent of patients for each QTc parameter for the following categories will be summarized:

QTc < 450, 450 to < 480, 480 to 500, and > 500 ms.

QTc change from baseline 30 to < 60 and ≥ 60 ms.

#### **10.5.11 Immunologic Biomarkers**

Associations between biomarkers and efficacy outcomes (OS, ORR, and PFS) may be analyzed on all patients with available biomarker data. Models to predict clinical activity based on combinations of biomarkers may also be investigated.

Additional post hoc statistical analyses not specified in the protocol or statistical analysis plan, such as alternative modeling approaches, may be conducted. All analyses are based on the availability of the data.

#### **10.5.12 Pharmacokinetic Analyses**

The concentration vs time will be collected for all patients treated with AM0010 in combination with nivolumab and used for exposure-response analyses (exposure-safety and exposure-efficacy) of selected safety and efficacy endpoints. Results of PK and exposure-response analyses will be reported separately.

### **10.6 Interim Analysis**

Interim analysis may be conducted to evaluate patients' safety profile.

## **11.0 INVESTIGATIONAL PRODUCT**

### **11.1 AM0010**

AM0010 will be manufactured and packaged by a third-party under the direction of Lilly and distributed using Lilly's/designee clinical trial drug distribution procedures. AM0010 is provided as a sterile, single use prefilled syringe, with a clear solution formulated at a concentration of 4 mg/mL.

Each patient (Arm 1) will receive weight-based doses of single use prefilled syringes, instruction for self-administration and an AM0010 dosing diary.

The AM0010 drug product is stored refrigerated. Refer to the product label for full storage instructions.

AM0010 should be stored in a secure location with limited access under controlled temperature conditions. Prefilled syringes should be stored in their original folding carton and should not be dispensed until patient is randomized or patient resupply is required.

The packaging lot number of AM0010 will be recorded on each patient's Drug Administration CRF.

Additional AM0010 details including labeling, storage, and preparation information are provided in the Pharmacy Guide. It should be noted that this manual may be updated/revised as additional information becomes available.

### **11.2 Compliance in Investigational Product Administration**

When investigational product is dispensed for administration to the patient during a trial, the Investigator or responsible person will determine the extent to which the patient complies with the recommended administration of the investigational product. The patient's investigational product compliance will be recorded on the drug administration case report form. Because this trial involves the self-administration of an SQ drug product, patients will need to complete an AM0010 dosing diary.

## **12.0 ETHICAL CONSIDERATIONS**

### **12.1 Local Regulations**

The trial must fully adhere to the principles outlined in “Guideline for Good Clinical Practice” (GCP) ICH E6 R2 Tripartite Guideline (June 2017). The Investigator will ensure that the conduct of the trial complies with the basic principles of GCP as outlined in the current version of 21 CFR, Subpart D, Part 312, “Responsibilities of Sponsors and Investigators,” Part 50, “Protection of Human Subjects,” and Part 56, “Institutional Review Boards.”

### **12.2 Informed Consent**

It is the responsibility of the Investigator, or a person designated by the Investigator, to obtain written informed consent from each patient participating in this trial after adequate explanation of the aims, methods, anticipated benefits, and potential hazards of the trial. In the case where the patient is unable to read, an impartial witness should be present during the entire informed consent discussion. After the patient has orally consented to participation in the trial, the witness’ signature on the form will attest that the information in the consent form was accurately explained and understood.

If new safety information results in significant changes in the risk/benefit assessment, the consent form should be reviewed and updated as necessary. All patients (including those already being treated) should be informed of the new information, should be given a copy of the revised form, and should give their consent to continue in the trial.

### **12.3 Institutional Review Board**

A copy of the protocol and proposed informed consent form, other written patient information, and any proposed advertising material related to patient recruitment must be submitted to the IRB for written approval. A copy of the written IRB approval of the protocol and informed consent form must be received by Lilly or its designee before the recruitment of patients into the trial and the shipment of investigational product.

The Investigator must submit and, where necessary, obtain approval from the IRB for all subsequent protocol amendments and changes to the informed consent document. The Investigator should notify the IRB of deviations from the protocol or SAEs occurring at the site and other AE reports received from Lilly in accordance with local procedures/IRB policies.

The Investigator will be responsible for obtaining annual IRB approval/renewal throughout the duration of the trial. Copies of the Investigator’s reports and the IRB continuance of approval must be sent to Lilly or its designee.

### **12.4 Documentation Requirements**

The Investigator is responsible for forwarding the following documents to Lilly or designee for review before trial initiation can occur:

- Signed and dated protocol signature page (Investigator's Agreement)
- Copy of the IRB approval of the protocol, consent form, and patient information sheet
- Up-to-date curricula vitae of the Principal Investigator and all co/sub-investigators
- IRB composition and/or written statement that IRB is in compliance with regulations
- Laboratory normal ranges and documentation of laboratory certification (or equivalent)
- Current patient/Investigator indemnity insurance
- Signed trial contract
- Completed FDA form 1572 (Laboratories providing primary and secondary endpoint data and any central laboratories for the trial must be listed on the form.)
- Completed Financial Disclosure statements for the Principal Investigator, all co/sub-investigators, and their spouses or legal partners and dependent children.

### **12.5 Patient Confidentiality**

The Investigator must ensure that the patient's confidentiality is maintained. On the case report forms or other documents submitted to Lilly or its designee, patients should be identified by their initials and/or a patient trial number only. Documents that are not for submission to Lilly (eg, signed informed consent forms) should be kept in strict confidence by the Investigator.

In compliance with Federal regulations/ICH GCP Guidelines, the Investigator and institution are required to permit authorized representatives of Lilly, of the regulatory agency(s), and the IRB direct access to review the patient's original medical records for verification of trial-related procedures and data. Direct access includes examining, analyzing, verifying, and reproducing any records and reports that are important to the evaluation of the trial. The Investigator is obligated to inform and obtain the consent of the patient to permit such representatives to have access to his/her trial-related records without violating the confidentiality of the patient.

## **13.0 ADMINISTRATIVE AND LEGAL OBLIGATIONS**

### **13.1 Protocol Amendments and Trial Termination**

Protocol amendments, except where necessary to eliminate an immediate hazard to patients, must be made only with the prior approval of Lilly. Agreement from the Investigator must be obtained for all protocol amendments and amendments to the informed consent document. The IRB must be informed of all amendments and give approval. The Investigator must send a copy of the approval letter from the IRB to Lilly.

Both Lilly and the Investigator reserve the right to terminate the trial according to the trial contract. The Investigator should notify the IRB in writing of the trial's completion or early termination and send a copy of the notification to Lilly.

### **13.2 Trial Documentation and Archive**

The Investigator shall maintain a list of appropriately qualified persons to whom he/she has delegated trial duties. All persons authorized to make entries and/or corrections on case report forms will be included on a Site Signature Log.

Source documents are original documents, data, and records from which the patient's case report form data are obtained. These include but are not limited to hospital records, clinical and office charts, laboratory and pharmacy records, diaries, microfiches, radiographs, and correspondence.

The Investigator and trial staff are responsible for maintaining a comprehensive and centralized filing system of all trial-related (essential) documentation, suitable for inspection at any time by representatives from Lilly and/or applicable regulatory authorities. These elements should include:

- Patient files containing completed CRFs, ICFs, and patient identification list
- Trial files containing the protocol with all amendments, Investigator's Brochure, copies of pre-trial documentation (Section 12.4), and all correspondence to and from the IRB and Lilly
- Proof of receipt, Investigational Product Accountability Record, Return of Investigational Product for Destruction, Final Investigational Product Reconciliation Statement, and all drug-related correspondence

In addition, all original source documents supporting entries in the CRFs must be maintained and be readily available.

No trial document should be destroyed without prior written agreement between Lilly and the Investigator. Should the Investigator wish to assign the trial records to another party or move them to another location, he/she must notify Lilly in writing of the new responsible person and/or the new location.

### **13.3 Trial Monitoring and Data Collection**

The Lilly representative and Regulatory Authority inspectors are responsible for contacting and visiting the Investigator for the purpose of inspecting the facilities and, upon request, inspecting the various records of the clinical trial (eg, CRFs and other pertinent data) provided that patient confidentiality is respected.

The Lilly monitor/designee is responsible for verifying the CRFs at regular intervals, approximately once per month, throughout the trial to verify adherence to the protocol, completeness, accuracy, and consistency of the data; and adherence to local regulations on the conduct of clinical research. The monitor should have access to patient medical records and other trial-related records needed to verify the entries on the CRFs.

The Investigator agrees to cooperate with the monitor to ensure that any problems detected in the course of these monitoring visits, including delays in completing CRFs, are resolved.

In accordance with ICH GCP and the Sponsor's audit plans, this trial may be selected for audit by representatives from Lilly Clinical Quality Assurance Department (or its designees). An inspection of site facilities (eg, pharmacy, drug storage areas, and laboratories) and a review of trial-related records will occur to evaluate the trial conduct and compliance with the protocol, ICH GCP, and applicable regulatory requirements.

If an anti-tumor treatment is initiated within 90 days of the last dose (AM0010/nivolumab), the start date of this treatment should be documented on the appropriate CRF, and no further recording of concomitant medications will occur unless it is to treat AM0010-related AEs.

To ensure the quality of clinical data across all patients and sites, a clinical data management review will be performed on patient data received at Lilly or its designee. During this review, patient data will be checked for consistency, omissions, and any apparent discrepancies. In addition, the data will be reviewed for adherence to the protocol and GCP. To resolve any questions arising from the clinical data management review process, data queries and/or site notifications will be sent to the site for completion and returned to Lilly or its designee.

The Principal Investigator will sign and date the indicated places on the CRF. These signatures will indicate that the Principal Investigator inspected or reviewed the data on the CRF, the data queries, and the site notifications, and agrees with the content.

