### **5.1 Treatment Arms**

Patients will be randomized in a 1:1 ratio into 1 of 2 arms according to histology type (squamous vs non-squamous) and smoking history (current smokers vs former smokers vs never smokers) as follows:

- Arm 1: Patients will receive AM0010 and nivolumab
- Arm 2: Patients will receive nivolumab alone.

Note: For the purposes of randomization, current smokers will include patients who are currently using any form of tobacco, former smokers will include patients with a prior history of any form of tobacco use, and never smokers will include patients with no history of any form of tobacco use.

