## **7.8 Continued Treatment**

### **7.8.1 Crossover**

At the time of disease progression (as assessed by the Investigator) patients randomized to trial Arm 2 may crossover to study Arm 1 to receive AM0010 and nivolumab. When progressive disease is noted on the scan for an ARM 2 patient, no more than 21 days should pass before the patient crosses over to ARM 1. The scans and/or clinical assessment at crossover will be used as a new baseline to determine response or PD on ARM 1.

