## 6. A Priori Statistical Methods

### 6.1. General Considerations

#### 6.1.1. Population

**Enrolled Population:** all patients who signed the informed consent form and were registered into the interactive web response system (IWRS).

**Intent-to-Treat (ITT) population:** all randomized patients per the IWRS.

Unless otherwise noted, all disposition analyses will be performed on the ITT population, all patient characteristic and efficacy analyses will be performed on the ITT population and all safety and exposure analyses will be performed on the safety population.

All analyses will be performed descriptively by treatment arm. Unless otherwise noted, all summary statistics on the ITT population will be performed by assigned treatment arm and all summary statistics on the safety population will be performed by actual treatment received.

**Per-Protocol Population:** all patients who are in the safety population and have no important protocol deviations.

The important protocol deviations which will result in exclusion from the Per-Protocol population are listed below. This is not an exhaustive list and may be amended over the course of the trial.

- patients with disease histology other than NSCLC
- patients with European Cooperative Oncology Group (ECOG) >1 at baseline
- patients who received more than one prior regimen in metastatic setting
- patients who do not have measurable disease at baseline
- patients receiving the incorrect randomized treatment assignment (any amount of duration)

**Response Evaluable Population:** all patients who are randomized and received any amount of study medication, have baseline adequate tumor assessment, and at least 1 post-baseline adequate tumor assessment.

**Safety Population:** all randomized patients who received any amount of study medication, AM0010 or nivolumab.

**PK Population:** all patients who are treated and with available serum time-concentration data from randomized patients.

**Biomarker Population:** all patients who are treated and with available biomarker data from randomized patients.

**ADA Evaluable Population:** all patients who are treated (in safety population), have baseline ADA (Anti-Drug Antibody) result, and at least one post-baseline ADA result.

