#### **6.4.6. Concomitant Medications**

All medications will be coded to the generic preferred name according to the current World Health Organization (WHO) drug dictionary. All concomitant medications will be summarized for the ITT population using the preferred name.

Selected concomitant medication such as steroid use will be summarized separately.

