### **6.6.5. Immune mediated AE**

Potential immune mediated AE, such as colitis, pneumonitis, endocrine and hepatic events will be summarized.

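### Once new anti-tumor treatment starts, only medication for AM0010-related AEs is recorded, so the late part of the by-arm concomitant-medication and steroid summary can be uneven

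*Protocol*

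**What the plan says.** **Recording rule.** Protocol 13.3 sets the trigger with both drugs named: "If an anti-tumor treatment is initiated within 90 days of the last dose (AM0010/nivolumab"). The consequence, in the same sentence, is that "no further recording of concomitant medications will occur unless it is to treat AM0010-related AEs". The exception names one drug only.

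**Who receives AM0010.** Protocol 5.1: "Arm 2: Patients will receive nivolumab alone". Under Protocol 7.8.1, at progression, "patients randomized to trial Arm 2 may crossover to study Arm 1 to receive AM0010 and nivolumab".

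**Use of the data.** SAP 6.4.6: "All concomitant medications will be summarized for the ITT population using the preferred name", and "Selected concomitant medication such as steroid use will be summarized separately". Under SAP 6.1.1, unless otherwise noted, "all summary statistics on the ITT population will be performed by assigned treatment arm". SAP 6.4.6 ends the medication summary neither at new anti-cancer therapy nor at crossover.

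**Relatedness.** For the combination arm, SAP 6.6.2 counts an AE as related if it is attributed to AM0010, to nivolumab, or to both. The exception in Protocol 13.3 covers only part of that set.

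**The concern.** Both arms receive nivolumab, so both are at risk of immune-mediated toxicity and of steroid treatment for it. Protocol 13.3 makes the recording of late medication depend on attribution to a drug that Arm 2 patients do not receive unless they cross over. The trial is open-label, so the attribution is made with knowledge of treatment.

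A reader of the SAP 6.4.6 tables would take a difference between arms as a difference in use. In the period after new therapy, part of it could come from the recording rule, and that part can only add to Arm 1 relative to Arm 2. Steroid treatment of AEs attributed only to nivolumab would also be under-counted in both arms.

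**Working it through.** The plan gives no figure on this point, so there is none to reproduce. The check is a comparison of the texts, followed by an illustration of size.

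**Step 1: what is recordable once the rule is triggered.** Before new therapy starts, the same recording rule applies to both arms. Afterwards:

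| Patient | Medication for an AM0010-related AE | Medication for an AE attributed only to nivolumab | Other medication |
|---|---|---|---|
| Arm 1 | recorded | not recorded | not recorded |
| Arm 2, crossed over | recorded | not recorded | not recorded |
| Arm 2, never crossed over | cannot arise | not recorded | not recorded |

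Crossover is read here as study treatment and not as a new anti-tumor treatment; Protocol 13.3 does not say so explicitly.

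**Step 2: whether the SAP removes the difference.** It does not. SAP 6.4.6 states no cut-off, and SAP 6.1.1 keeps crossover patients in Arm 2 for ITT summaries. Elsewhere the SAP separates crossover data: Table JZGD.6.2 leaves the crossover period out of cumulative dose, and SAP 6.7.4 censors Arm 2 AEs at crossover. The medication summary has no corresponding rule.

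**Step 3: illustration of size.** Suppose true steroid use after new therapy is equal in the two arms. Let

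- n = 25 patients per arm (Protocol 3.2);
- q = share who start new therapy within 90 days (assumed 20% to 60%);
- s = share of those who then start a steroid (assumed 10% to 20%);
- a = share of that use attributed to AM0010 among patients exposed to it (assumed 0% to 100%);
- c = share of the affected Arm 2 patients who had crossed over (assumed 0% to 50%).

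Then:

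- true starts per arm = n·q·s;
- recorded in Arm 1 = n·q·s·a;
- recorded in Arm 2 = n·q·s·c·a;
- artificial gap = n·q·s·a·(1 − c).

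Results:

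- True starts per arm: from 25 × 0.2 × 0.1 = 0.5 to 25 × 0.6 × 0.2 = 3.0.
- Middle case (q = 0.4, s = 0.2, a = 0.5): true starts 25 × 0.4 × 0.2 = 2.0. The gap is 2.0 × 0.5 = 1.0 patient without crossover and 2.0 × 0.5 × 0.5 = 0.5 with half crossed over.
- Largest gap (q = 0.6, s = 0.2, a = 1, c = 0): 3.0 patients.
- Smallest gap (a = 0): zero, whatever the other inputs.

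One patient in 25 is 4 percentage points. Apart from n, every input is an assumption; the documents supply none of them.

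**The case against.** The strongest case on the other side is that the effect is narrow and of low consequence. Only the period after new therapy is affected, and Protocol 9.3 asks for follow-up assessments to be completed before that therapy starts. SAP 6.4.6 sits under patient characteristics, and SAP 6.1.1 makes all analyses descriptive. All of this stands, and it sets the severity. It does not remove the unequal rule.

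Four stronger readings are tempting, and the documents do not support them.

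- *Recording stops throughout Arm 2 and carries on in Arm 1.* Crossover patients remain in Arm 2 for the ITT summary and can meet the exception. In Arm 1 everything outside the exception stops as well.
- *The summary must show more steroid use in Arm 1.* The trial rationale (Protocol 1.3) says AM0010 given alone caused no autoimmune toxicity. Investigators may therefore attribute immune-mediated events to nivolumab, and that steroid use then goes unrecorded in both arms. The gap can be zero.
- *The imbalance can be read from the share of the 90-day window covered in each arm.* This sets all medication in Arm 2 against only AM0010-related medication in Arm 1, which is not like for like. The 90 days are also a trigger, not a stated recording period: concomitant medication is listed at the 28-day end-of-treatment visit (Protocol 7.9) but not in the follow-up list (Protocol 7.10), and the extent of the Appendix A arrow cannot be seen in the text available.
- *The nivolumab toxicity signal itself is lost.* Protocol 13.3 restricts medication records, not AE records. Protocol 9.3 still requires related SAEs after 30 days to be reported, and SAP 6.6.2 counts related serious events as treatment-emergent at any time. The planned summary in SAP 6.6.5 ("Potential immune mediated AE, such as colitis, pneumonitis, endocrine and hepatic events will be summarized") concerns AEs, so this rule does not restrict its source data.

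**Conclusion.** The concern holds in a limited form. After a new anti-tumor treatment starts within 90 days of the last dose, what can be recorded depends on exposure and attribution to AM0010, and SAP 6.4.6 carries those records into a by-arm summary without a cut-off. Any resulting distortion runs toward more recorded late use in Arm 1. It can occur but need not, and its size cannot be derived from the documents; the range of 0 to 3 patients per 25 rests on assumed inputs and equal true use. The firmer finding is that treatment of AEs attributed only to nivolumab goes unrecorded in both arms after the trigger. Severity is minor: the summary is descriptive, and neither the primary nor any secondary efficacy endpoint uses it.

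**What to change.** **Protocol 13.3.** Change the exception so that it covers medication for AEs related to study treatment, meaning AM0010 and/or nivolumab, with the same wording for both arms. This also brings the rule into line with the relatedness definition in SAP 6.6.2. Cost: one phrase in the protocol and CRF guidance, and a few extra medication entries.

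**SAP 6.4.6, for data already collected.** End both the concomitant-medication summary and the steroid summary at the start of new anti-cancer therapy in both arms and, for Arm 2, at crossover if that comes first. A cut at new therapy alone would leave medication from the AM0010 period of crossover patients in the Arm 2 column. The crossover cut matches how the SAP already treats dose (Table JZGD.6.2) and AEs (6.7.4). Cost: a cut-off rule in the SAP and slightly less late data; no new data are needed.
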